1.1 Overview

This prospective, randomized, controlled phase III nephrology study will determine whether rituximab is non-inferior to cyclosporine in inducing long-term remission of proteinuria in patients with idiopathic membranous nephropathy (IMN.) Subjects are randomized to open-label courses of treatment: IV rituximab (RTX), 1000 mg (2 infusions, 14 days apart), or oral cyclosporine (CSA) 3.5 to 5 mg/kg/day. Subjects are evaluated at 6 months; those that meet treatment response criteria will continue study medication and receive either 2 further infusions of RTX or a further 6 months of daily CSA treatment. Throughout the study period, laboratory and safety parameters will be collected and documented.

Study Hypothesis: B cell targeting with Rituximab is non-inferior to Cyclosporine in inducing long-term remission of proteinuria.

Comparison(s): IV rituximab (RTX), 1000 mg (2 infusions, 14 days apart; repeated at 6 months if a substantial reduction in proteinuria (equal to or >25%) is seen at 6 months) or oral cyclosporine (CSA) 3.5 to 5 mg/kg/day for 6 months (continued for another 6 months if a substantial reduction in proteinuria (equal to or >25%) is seen at 6 months).

SPECIFIC AIMS:

The specific aims of this Phase III trial are to test the hypothesis;

1. That B cell targeting with Rituximab is **non-inferior to** Cyclosporine in inducing **long-term remission** (complete or partial) of proteinuria in patients with IMN.
2. That B cell targeting with Rituximab **reduces the number of relapses (efficacy in sustaining remission) and increases the time to relapse when compared with treatment with Cyclosporine.**
3. That B cell targeting with Rituximab is **as effective as** Cyclosporine in inducing **complete or partial remission** of proteinuria in patients with IMN during the active treatment phase.
4. That B cell targeting with Rituximab has a better side effect profile and improved quality of life when compared with treatment with Cyclosporine in patients with IMN.

BACKGROUND AND SIGNIFICANCE

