The goal of this proposal is to conduct a prospective randomized controlled phase III study comparing Rituximab (RTX) to Cyclosporine (CSA) in the treatment of patients with IMN. Once a patient with IMN and proteinuria $\geq 5\text{g}/24\text{h}$ is identified, meets other entry criteria and consents to the study, he/she will receive a minimum of 3 months of conservative therapy aimed at maximizing Angiotensin II blockade (run-in phase). If at the end of this period the patient still meets entry criteria he/she will be randomized into a 12-month treatment period, and a subsequent follow-up of 12 months. Efficacy of treatment will be assessed by remission status (based on changes in proteinuria) at 24 months from randomization. Patient safety will be assessed via collection of adverse event data and evaluation of pre- and post-treatment laboratory data. At the 6-month post-randomization visit, patients who have been randomized to either CSA or RTX but who do not have a reduction in proteinuria $\geq 25\%$ (confirmed on repeat measurements within 2 weeks) will be considered treatment failures and exit the study. Data from that point onward will be censored. Patients in the RTX group who have a reduction in proteinuria of equal to or $>25\%$ at 6 months will be given another identical course of RTX (1g x 2). This treatment regimen was chosen given our initial data that suggested a percentage of our cohort appeared to respond to an additional course of therapy. Data from our 2 pilot studies showed that RTX is out of the circulation by month 2 in the majority of patients and B cells have recovered by month 3 in patients treated with RTX 1g x 2 (the regimen chosen for the study). Thus, at 6 months, patients in the RTX arm are completely, at least as best as we can measure, free of immunosuppression, and hence the second course should not be associated with additive toxicity. The same definition of response will apply to the CSA arm at 6 months. An equal to or $>25\%$ reduction in proteinuria will dictate continuation of the CSA for an additional 6 months (total of 12 months of full dose CSA). This assessment at six months allows a balance between risk-benefit in both arms. The protocol provides similar exposure to immunosuppression in both arms and allows an early exit for patients related to safety issues by providing a lack of efficacy (futility) end point at 6 months.

Primary endpoint

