For those patients in the Cyclosporine arm, **Cyclosporine trough level measurements will be done every 2 weeks +/- 3 days after initiation of Cyclosporine until levels are stable and at target. Potassium and creatinine will also be checked in conjunction with CSA level. If Cyclosporine dose is changed during treatment, potassium, creatinine and CSA level will be rechecked every 2 weeks +/- 3 days until levels are stable and at target.** Cyclosporine levels will also be assessed whenever serum creatinine rises by $>30\%$ without a recognizable reason such as volume depletion, additional drugs, sepsis, etc. Patients who cannot tolerate the medications and/or who are treatment failures at 6 months will exit the study at 6 months (i.e., the 6 month visit and accompanying data collection should still occur). Patients who go in to complete remission will discontinue study drug but will continue with full visit follow-ups until month 24 as scheduled. However, the therapeutic/management plan for these patients will be solely at the discretion of the managing nephrologist although while in CR no further immunosuppressive therapy is recommended. Likewise, patients who relapse from either a partial or complete remission or who are not in partial or complete remission by the end of the treatment period (i.e., 12 months) will continue with the visit schedule, but the therapeutic/management plan will be solely at the discretion of the managing nephrologist. Finally, for patients who temporarily stop taking Cyclosporine, there are three possible scenarios:

1. Patients who discontinue Cyclosporine for < 2 weeks may simply be restarted on the study drug and continue to fully participate in the trial. The treatment is to be restarted at its former dose and the patient returned to the regularly scheduled follow-ups including the periodic sampling for assessing potassium, creatinine and CSA trough levels.
2. Patients who discontinue Cyclosporine for ≥ 2 weeks, but < 4 weeks may also be restarted on the study drug at its former dose and fully participate in the trial, but the temporary discontinuance will be logged as a protocol deviation and the missed treatment days will be made up at the end of month 12. This is to ensure that all patients receive approximately 12 months of treatment with study drug.

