Investigators in the study will be blind to the results of anti-PLA2R antibodies until the study is completed. The rationale is to avoid bias in the treatment of these patients. Although ideally patients would be stratified to the different arms based on the results of their initial anti-PLA2R test in order to avoid potential imbalance this will not be possible for practical and financial reasons. Given the relatively small number expected to be negative, it is unlikely this will bias the balance between positive and negative patients at randomization.

Histopathology

Prior to randomization, a report documenting the results of the histology review including, light microscopy, immunofluorescence and electron microscopy results, as well as percentage of global and segmental glomerular sclerosis, tubulo-interstitial index, and immunofluorescence findings will be submitted to the DMCC and reviewed by the study P.I.

Following randomization, biopsy slides will be centrally reviewed on an on-going basis (but as soon as possible following randomization) by the Pathology Department at Mayo Clinic Rochester and/or the Pathology Department at the University Hospital Network, Toronto.

Quality of life measures

Psychosocial response to illness and its treatment may play an important role in overall adjustment and illness management. Research from a variety of chronic illness populations, including steroid resistant FSGS and chronic kidney disease (CKD), has consistently linked physical and psychosocial variables with health outcomes. These findings highlight the significant burden experienced by adults with uncontrolled nephrotic syndrome. Little is known about the impact of MN or its treatment on patient reported outcomes. Due to the severity of this disease and the potential risk for progression in these patients, psychosocial factors may play an important role in understanding their response to treatment. In addition to evaluating the safety and efficacy of RTX and CSA, it is essential to assess the individual's perception of his/her quality of life relative to disease status and therapeutic response. Quality of life will be assessed by patient self-report using the modified KDQOL questionnaire form at Time 0, 6, 12 and 24 months.

Table 2a: Test Schedule and Monitoring for Cyclosporine Treatment Arm

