
Statistical and Analytical Plan: All demographics and entry laboratory data will be summarized by treatment group. Frequency distributions will be used to describe categorical values and basic summary statistics (mean, standard deviation, median, and inter-quartile range) will be used to describe continuous values. To provide more reliable estimates and minimize the “regression to the mean effect” duplicate urine measurements obtained at baseline (Time 0), 6, 12, 18 and 24 months will be averaged. The chi-square test and logistic regression will also be used to compare the percent of patients with remission at 6, 12, 18, and 24 months adjusting for treatment center and the baseline

proteinuria (UP<8g/24h vs >=8g/24h). Odds ratios and associated 95% confidence intervals will be estimated. The formal test for the primary endpoint will be based on the significance of the treatment group factor in the logistic regression model for UP failure at month 24. The Wilcoxon rank-sum test and ordinal logistic regression will be used to compare the ordered remission status outcome (1=CR, 2=PR, 3=NR) between treatment groups. Longitudinal methods for categorical outcomes (e.g. generalized estimating equation or GEE models) will be used to compare remission status profiles between treatment arms. Unless otherwise noted, all tests will be two-sided with alpha level 0.05.

For repeated measures such as urine protein, individual rates of change will be estimated using within-patient linear regression analyses (including data from all visits). Because of the non-linearity of the changes in proteinuria log transformation estimates will be used. Renal function readings will be censored at initiation of dialysis or renal transplant. Additionally, mixed effects models, assuming a random center effect, and a random slope of creatinine clearance and/or reciprocal of creatinine and intercept for each patient will be fit using data from all visits. These models allow comparison of the average slope between groups, while taking into account that each patient's slope may be based on a variable number of readings. Treatment group comparisons regarding quality-of-life scales will be done using repeated measures analyses and mixed effects models.

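### KDQOL after month 6 is missing by design for every treatment failure, and the quality-of-life model rests on an unstated assumption that the planned data cannot test

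*Combined protocol and SAP*

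**What the plan says.** Aim 4 (Specific Aims) is that rituximab "has a better side effect profile and improved quality of life when compared with treatment with Cyclosporine", and KDQOL is a listed secondary endpoint. The section on quality of life measures sets the schedule: "Quality of life will be assessed by patient self-report using the modified KDQOL questionnaire form at Time 0, 6, 12 and 24 months".

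Under Overall Research Design and Methods, patients in either arm without a confirmed proteinuria reduction of at least 25% at month 6 "will be considered treatment failures and exit the study. Data from that point onward will be censored". Patient Monitoring and Evaluation repeats the rule but keeps the assessment at that visit: "treatment failures at 6 months will exit the study at 6 months (i.e., the 6 month visit and accompanying data collection should still occur".

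The Statistical and Analytical Plan then says: "Treatment group comparisons regarding quality-of-life scales will be done using repeated measures analyses and mixed effects models". It names no covariates for this model, no main time point, no missing-data assumption and no sensitivity analysis. The 18-month substitution, and the counting of other missing patients as failures, apply only to the binary primary endpoint. The follow-up encouraged under Stopping Points for Medications covers patients who stop study drug by choice or are withdrawn for adverse events. It does not name month-6 failures.

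The sample size section places the quality-of-life comparison within the treatment period, which Patient Monitoring and Evaluation defines as the first 12 months. It also claims 80% power for a difference of 0.6 SD with 63 patients per arm.

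**The concern.** Whether a patient has a month-12 or month-24 score is decided by proteinuria response. The protocol itself points to the "significant burden experienced by adults with uncontrolled nephrotic syndrome", which is close to the state that leads to exit.

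A likelihood-based mixed model predicts a missing later score from the patient's own earlier KDQOL scores, using the relation seen in patients who stayed. Response is not in the model as described. If response carries information about later quality of life beyond what the Time 0 and month-6 scores already hold, the prediction for failures is wrong. Because no failure is measured after exit, nothing in the planned data would show it. At stake is the between-arm comparison for Aim 4.

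**Working it through.** **The plan's own figure.** With 63 per arm, the standard error of an unadjusted difference is sqrt(2/63) = 0.178 SD. For 0.6 SD at two-sided 0.05: 0.6/0.178 = 3.37, and 3.37 - 1.96 = 1.41, so power is 92%, not 80%. Power of 80% corresponds to (1.96 + 0.84) x 0.178 = 0.50 SD. The stated figure is therefore conservative, and 0.6 SD is a generous yardstick for bias.

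**Inputs.** From the documents: 63 per arm, two-sided alpha 0.05, exit of failures after the month-6 assessment, and month 12 as the last KDQOL visit in the treatment period. Assumed, because the documents give no value: correlation of 0.6 between any two visits, failure share f of 10% to 40% per arm, and residual deficit g. Here g is the amount, in SD, by which failures' month-12 score falls below what their own Time 0 and month-6 scores predict.

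**Prediction weights.** With correlation 0.6, the Time 0 and month-6 scores each get weight 0.6/1.6 = 0.375. As an illustration of g, suppose retained patients gain 0.36 SD by month 6 and 0.60 SD by month 12, and failures gain nothing. The month-6 shortfall predicts a later shortfall of only 0.375 x 0.36 = 0.135 SD, so g = 0.60 - 0.135 = 0.465 SD.

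**Bias.** Month-12 bias toward arm B = fB x gB - fA x gA. For 10% v 30% with g = 0.3 in both arms: 0.30 x 0.3 - 0.10 x 0.3 = 0.06 SD. With g = 0.6: 0.18 - 0.06 = 0.12 SD. A large simulation (400,000 per arm) agreed with the formula to about 0.002 SD.

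**Error rate.** With the true month-12 difference set to zero, 4,000 simulated trials of 63 per arm gave a standard error of 0.19 to 0.20 SD. The chance of a significant result favouring B is Phi(mean estimate/SE - 1.96). For 10% v 30% and g = 0.6: Phi(0.121/0.190 - 1.96) = 9.2%.

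| Failures, A v B | g in A / B (SD) | Bias toward B (SD) | False result favouring B (nominal 2.5%) |
|---|---|---|---|
| 20% v 20% | 0.6 / 0.6 | 0 | 2.3% |
| 10% v 30% | 0 / 0 | 0 | 2.4% |
| 15% v 25% | 0.3 / 0.3 | 0.03 | 3.5% |
| 15% v 25% | 0.6 / 0.6 | 0.06 | 4.8% |
| 10% v 30% | 0.3 / 0.3 | 0.06 | 4.8% |
| 10% v 30% | 0.6 / 0.6 | 0.12 | 9.2% |
| 10% v 40% | 0.6 / 0.6 | 0.18 | 14.2% |
| 10% v 30% | -0.3 / -0.3 | -0.06 | 1.2% |
| 25% v 25% | 0.6 / 0.2 | -0.10 | not calculated |
| 20% v 30% | 0.6 / 0.2 | -0.06 | not calculated |

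**Complete-case variant.** The plan's wording also permits a repeated-measures analysis of patients with all visits. If month-6 KDQOL correlates 0.4 with the failure criterion (assumed), that analysis favours the higher-failure arm by about 0.07 SD at 10% v 30%, even with g = 0.

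**With continued collection.** When failures' month-12 scores are observed, the simulated mean is within 0.005 SD of the truth in every scenario run.

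**The case against.** A reader might infer that the model fills in failures from responders and so must favour the arm with more failures. The documents do not support that, for four reasons.

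- The month-6 visit is kept for failures, so the model uses each failure's own Time 0 and month-6 scores. Bias arises only from what those scores miss.
- Retained patients are not all responders in any strong sense. A fall from 10 to 7.5 g/24h keeps a patient in the study without meeting Table 1's definition of remission. Patients not in remission at month 12, and those who relapse, also keep the visit schedule. This makes a large g less likely.
- Nothing says exit rates will differ. Aim 3 expects similar efficacy during active treatment, and the sample size section describes the 12-month remission rates as much alike.
- The preliminary studies describe a gradual fall in proteinuria after rituximab. That could raise rituximab exits at month 6, but it could also mean that those patients improve later, which is the reversed case.

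The bias is also modest: 0.06 to 0.12 SD is about a third to two thirds of the unadjusted standard error of 0.178 SD. All of this stands against a claim of known direction or large size. None of it supplies the missing scores, states the assumption or makes it testable.

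**Conclusion.** The point holds in a conditional form. KDQOL at months 12 and 24 is absent by design for every month-6 failure. The planned analysis is valid only if those patients' later scores follow from their own Time 0 and month-6 scores.

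If failures do worse than predicted to a similar extent in both arms and exit rates differ, the comparison is biased toward the arm with more failures. With equal rates and equal deficits, or with no residual deficit, there is no bias. It can reverse if failures improve after exit or if deficits differ by arm.

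For 10% v 30% exits and g of 0.3 to 0.6 SD, the month-12 bias is about 0.06 to 0.12 SD and the one-directional error about 5-9%. Exit rates, g and the correlation are all assumptions. Month 12 is the visit that matters most, because the plan sets this comparison in the first 12 months; month 24 is affected only if the model uses it. A reader should not carry this over to the primary non-inferiority result, which has its own rule for missing patients and does not depend on KDQOL.

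**What to change.** Keep collecting KDQOL at months 12 and 24 from month-6 failures, by mail or telephone, and include those scores in the model.

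For scores still missing:

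- State the missing-data assumption and name month 12 as the main affected time point.
- Add month-6 proteinuria response as an auxiliary variable. This needs some returned questionnaires from failures; with none, the model can only extrapolate from retained patients.
- Run a delta-adjusted sensitivity analysis that lowers or raises failures' predicted scores over a stated range, separately by arm, since the bias depends on each arm's deficit.
- Report the month-6 contrast alongside, because KDQOL is scheduled there before exit. Making it the main contrast would be a trade-off, as it drops the second half of the treatment period. Holding failures at an earlier score is a weaker choice than the delta adjustment.

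The cost is two questionnaires each for an assumed 13 to 38 patients (10% to 30% of 126) and a little more analysis work. The downside is incomplete return from patients who have left the study.
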